1. BACKGROUND

Elder mistreatment (EM) is a major public health problem with estimated prevalence in the United States ranging from 27.9% to 62.3% for emotional abuse and 3.5%–23.1% for physical abuse among older adults with cognitive impairment (CI). EM consists of physical, emotional, sexual and financial abuse as well as neglect committed by a person in a position of trust to the older adult. It causes serious adverse outcomes for its victims including injury, increased service utilization, mental distress and the risk of mortality. A major barrier in overcoming EM is the inability to accurately identify EM victims. It is estimated that only 1 in 24 cases become known to authorities. There are several perceived barriers to self-disclosure (informing others about the EM experiences) that limit help-seeking behaviors, including fear of nursing home placement, of losing autonomy or a caregiver, and of getting an abusive family member in legal trouble. As a result, reporting of EM remains low and providers often miss the opportunity to identify EM at point-of-care.

In our parent project, we used Digital Health frameworks to develop the Virtual cOaching in making Informed Choices on Elder Mistreatment Self-Disclosure (VOICES) tool. This is a new and innovative digital health tool that screens, educates, and motivates older adults to make an informed decision about self-identification (recognizing that they themselves are victims) and self-disclosure of elder mistreatment. In a prior clinical study at Yale Emergency Department (IRB Protocol ID:2000023799 and Submission ID:CR00008317), we developed an innovative digital health tool that runs on tablets called VOICES that screens, educates, and motivates older adults to make an informed decision about self-reporting of elder mistreatment. 1,002 older adults have used the VOICES tool so far without any issues. Study participants have demonstrated signs of feasibility, acceptance, demand, and full completion of the tool for those who consented to participate. There is an opportunity to expand the use of the VOICES tool to a more vulnerable older adult populations, such as older adults in primary care settings.

2. AIMS

The primary objective of this study is to determine whether the VOICES tool is feasible for identifying suspicion of elder mistreatment among older adults in primary care settings.

3. STUDY DESIGN

The design is a single arm trial to conduct a feasibility study across five important areas including: acceptability, demand, implementation, practicality, and limited efficacy. The primary outcomes are participation and usage. Participation will be determined by the number of patients enrolled in VOICES. Usage will be determined by the number of

patients enrolled in the study that complete the VOICES tool. Over the course of this project, we recruited 80 subjects over 7 months.

4. OUTCOMES

The primary and Other Pre-Specified Outcome Measures are summarized in Table 1.

Table 1. Primary and Other Pre-Specified Outcome Measures		
Domain	Measure (P,O)	Source and Frequency
Implementation	Participation. Participation will be determined by the ratio of participants who are successfully enrolled to the total number of eligible patients. (P)	Study enrollment records
	Usage. Usage will be determined by the number of consented participants enrolled in the study who used VOICES to completion (P)	VOICES tool completion records
Acceptability	Participant satisfaction measured using post-use satisfaction survey with two 5-point Likert response set scales, developed by the research team (O)	Self-report, once per participant
Demand	Measured by the % of the patients who self-identified with elder mistreatment and the % who receive the Brief Negotiation Interview (BNI) portion of VOICES.	Measured by VOICES tool, once per participant
Practicality	Average time to consent & orient participants to the tool (O)	RA measurement, once per participant
	Average time needed to complete VOICES (O)	RA measurement, once per participant
	Average time patients perceived time of VOICES	Self-report, once per participant
Efficacy of the Brief Negotiation Interview	Measured as % participants that change their self-identification response after completing the educational component (O)	Measured by VOICES tool, once per participant
Efficacy of Self-Identification on Self-Disclosure	Measured as % of patients who disclose among those who self-identified (O)	Measured by VOICES tool, once per participant
Accuracy	Measured as percent of classified EM cases that were positive based on social worker assessment, and those referred to Adult Protective Services (APS). (O)	Measured by the outcome of the social worker assessment and by the outcome APS evaluation.

EM: Elder Mistreatment; BNI: Brief Negotiation Interview; APS: Adult Protective Services

4.1 Primary Outcome

Implementation in Terms of Participation. Participation will be determined by the ratio of participants who are successfully enrolled to the total number of eligible patients.

Implementation in Terms of Usage. Usage will be determined by the number of consented participants enrolled in the study who used VOICES to completion.

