5.3.1 Number of Participants

The number participants to be recruited is 80 participants.

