5.3.2 Eligibility Criteria/Vulnerable Populations

In order to be eligible to participate in this study, an individual must meet all of the following criteria:

1. Age 60 or above
2. Living in Community Dwelling
3. Able to consent and communicate in English
4. Has no risk of COVID-19
5. Agrees and able to use the iPad
6. Stated willingness to comply with all study procedures and availability for the duration of the study
7. Provision of signed informed consent, or assent if LAR provides consent

An individual who meets any of the following criteria will be excluded from participation in this study:

1. Subjects who live in nursing homes or other long-term care setting
2. At the discretion of the clinician, patient will be excluded if they cannot safely undergo the studies required for participation
3. Patient refusal to participate
4. Severe cognitive, hearing, or vision impairment

6 Methods

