7. ANALYTIC PLAN
 - 7.1. Analysis of Primary Outcome
 - 7.2. Analysis of Other Pre-Specified Outcome Measures

REFERENCES

STUDY SUMMARY (revised 5/16/2023)

Title	The Feasibility of the VOICES Digital Health Tool for Elder Mistreatment Screening in the Primary Care Setting
Study Design	The design is a single arm trial to develop the digital intervention and conduct a feasibility study across five important areas including: acceptability, demand, implementation, practicality, and limited efficacy.
Study Duration	7 months
Trial Sites	Yale Internal Medicine Associates (YIMA).
Objective	The primary objective of this study is to perform a feasibility evaluation of the VOICES screening tool among 80 older adults in primary care settings.
Number of Subjects	Over the course of this project, we recruited 80 participants.
Main Inclusion Criteria	
Inclusion Criteria:
 
 1. Age 60 or above 2. Living in Community Dwelling 3. Able to consent and communicate in English 4. Has no risk of COVID-19 5. Agrees and able to use the iPad 6. Stated willingness to comply with all study procedures and availability for the duration of the study 7. Provision of signed informed consent, or assent if LAR provides consent
Intervention	Our intervention is innovative because it utilizes best practices, and innovations in the design and development of digital health to create the one of its kind VOICES EM Intervention. As an easy-to-use, user-friendly EA intervention that runs on tablets with the information and messages displayed on the screen and spoken through headphones for privacy. VOICES delivers content specifically designed to target three factors (attitudes, subjective norms, perception of control) while providing accurate education on EM and APS response and dispelling myths and stereotypes surrounding victimization. VOICES will address perceptions of control making it easy to self-report and ask for help. Another innovative feature of VOICES is the ability to deliver health information through the use of digital tools, multimedia, and digitally guided interviews to older adults to increase awareness of EM.
Duration of Intervention	One session 8.8 minutes on average
Primary Outcome	The primary outcomes are participation and usage. Participation will be determined by the number of patients enrolled in VOICES. Usage will be determined by the number of patients enrolled in the study that complete the VOICES tool.

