7 ANALYTIC PLAN

7.1 Analysis of Primary Outcome:

Implementation in Terms of Participation. Participation will be determined by the ratio of participants who are successfully enrolled to the total number of eligible patients. The numerator, denominator, frequencies and 95% confidence intervals will be reported.

Implementation in Terms of Usage. Usage will be determined by the number of consented participants enrolled in the study who used VOICES to completion. The numerator, denominator, frequencies and 95% confidence intervals will be reported.

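### Primary Participation is a ratio in three places in the SAP and a count in two, and its denominator is not tied to a meaning of *eligible* under which refusals can lower it

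*SAP*

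**What the plan says.** Participation is one of two primary outcomes. SAP Table 1, 4.1 and 7.1 all define it as a ratio: "Participation will be determined by the ratio of participants who are successfully enrolled to the total number of eligible patients". SAP 7.1 adds the reporting rule: "The numerator, denominator, frequencies and 95% confidence intervals will be reported". The SAP Study Summary and Section 3 use a different form: "Participation will be determined by the number of patients enrolled in VOICES".

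The numerator is 80. Protocol 5.3.1 sets the target ("The number participants to be recruited is 80 participants"), and SAP Section 3 reports that 80 were recruited over 7 months.

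The SAP does not say whom the denominator includes. The protocol uses the word *eligible* in two ways:

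- **Formal list (Protocol 5.3.2).** Inclusion 5 is "Agrees and able to use the iPad". Inclusion 6 is "Stated willingness to comply with all study procedures and availability for the duration of the study". Inclusion 7 is signed consent, or assent where a legally authorized representative (LAR) consents. Exclusion 3 is "Patient refusal to participate". The SAP Study Summary repeats the inclusions. The first bullet of Protocol 6.3.4 has the research assistant (RA) screen for eligibility only once the patient wants to join.
- **Working usage.** Protocol 6.3.3 lets staff telephone eligible patients before any consent. The second bullet of 6.3.4 names consent alongside meeting the criteria. Protocol 6.3.5 treats being eligible and wanting to participate as two separate conditions.

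Table 1 gives only study enrollment records as the source for Participation.

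**The concern.** A participation ratio in a feasibility study should show how many of the patients who could have taken part did so. If refusal, unwillingness, not agreeing to use the iPad or lack of consent makes a patient ineligible, those patients leave the denominator together with the numerator. The ratio then cannot register the barriers it is meant to measure. The count form has no denominator at all, so the confidence interval required by 7.1 cannot be computed from it.

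The study asks how far VOICES can be delivered in this clinic (Protocol 4.1 and 5.2.1) and is meant to guide a later pilot (Protocol 5.1). Because the analysis is descriptive, the reported proportion is the result. As the SAP stands, the same recruitment could be reported as about 100%, as a much lower uptake, or simply as 80.

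**Working it through.** **Inputs.** Enrolled = 80 (SAP Section 3). Criteria are from Protocol 5.3.2, and the order of steps from Protocol 6.3.4. The documents give no number approached, eligible or refusing, so every denominator above 80 below is assumed. Intervals are exact (Clopper-Pearson) 95%.

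**The plan's own precision figure.** SAP 6.1 states a width of at most 0.228 for a proportion at N = 80. The exact interval at 40/80 is 0.386 to 0.614, width 0.228, and this is the largest width over all counts from 0 to 80. The figure reproduces. For Participation, 80 is the numerator and not the sample size, but the bound still holds: with 80 enrolled, the largest exact width over denominators from 80 to 2000 is 0.175, at 80/118. The precision statement is therefore not part of the problem.

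**Formal list.** Let A be patients approached, R those who refuse or do not agree, F those who fail another listed criterion, and k those who consent and meet the list but are not enrolled.

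- Eligible = A − R − F.
- Enrolled = A − R − F − k = 80, so eligible = 80 + k.
- Participation = 80/(80 + k). R does not appear.

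With k = 0 the ratio is 80/80 = 100%. The lower limit is 0.025^(1/80) = 0.955, so the interval is 95.5% to 100%.

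The documents describe one route to k > 0: a patient consents and the LAR or caregiver then stays in the room. That rule is not in the 5.3.2 list. Protocol 3.2.1 and 6.1.2 place it after consent. An assumed k = 2 would give 80/82 = 97.6%. However, 6.1.2 and 6.3.5 call such patients not eligible, and 3.2.1 calls them excluded. If they are removed on that ground, k returns to 0.

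**Pre-consent reading.** Suppose refusers who otherwise qualify stay in the denominator, with no other losses:

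| Assumed denominator | Implied refusals | Formal list (k = 0) | Pre-consent ratio | Exact 95% CI | Count form |
|---|---|---|---|---|---|
| 100 | 100 − 80 = 20 | 80/80 = 100% | 80/100 = 80% | 70.8% to 87.3% | 80 |
| 200 | 200 − 80 = 120 | 80/80 = 100% | 80/200 = 40% | 33.2% to 47.1% | 80 |
| 400 | 400 − 80 = 320 | 80/80 = 100% | 80/400 = 20% | 16.2% to 24.3% | 80 |

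For these assumed denominators the choice of reading moves the result well beyond the sampling interval. Only the pre-consent ratio changes with uptake.

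**The case against.** The strongest reply is that the intended meaning is clear enough. Protocol 6.3.3, 6.3.4 (second bullet) and 6.3.5 keep eligibility apart from willingness, and an enrolled-to-eligible ratio has a purpose only on that reading. This stands as evidence of intent. A reader might infer that the plan means to report 100%, or is bound to; the documents do not support either. The result at or near 80/80 is what the formal list gives when applied literally. What remains is that the SAP never adopts the pre-consent meaning for the outcome, while the only complete list of criteria points the other way.

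The count may be shorthand. Usage is worded similarly ("Usage will be determined by the number of consented participants enrolled in the study who used VOICES to completion"), yet 7.1 gives it a denominator and an interval, and the sections that define and analyse the outcome all use the ratio for Participation. This largely stands, so the count wording is the smaller part of the point. Nor is the count empty: 80 recruited in 7 months, against the 8 months in Protocol 6.4.2, says something about accrual. It says nothing about uptake among those asked.

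A third reply is that little harm can follow. The analysis is descriptive, no test or threshold uses the result, and the numerator and denominator required by 7.1 would show 80/80 openly. That limits the severity. It would not tell the reader how many patients declined.

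Finally, a denominator of everyone who meets all the non-volitional criteria may not be computable. Refusers are not screened under 6.3.4. The record-review variables in Protocol 7.1 do not include COVID-19 risk, iPad ability or clinician discretion. Contact can come through several routes. The HIPAA waiver is for recruitment only. All of this stands and shapes the fix.

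**Conclusion.** The point holds and should be fixed. The SAP words a primary outcome in two ways and does not tie the ratio's denominator to either of the protocol's meanings of *eligible*. Under the formal criteria refusals cannot lower the ratio. It is 80/80 (95.5% to 100%), or slightly lower if a few consented patients whose LAR or caregiver stayed are counted as eligible. Under the pre-consent meaning, which is probably the intended one, it could be 80%, 40% or 20% at denominators of 100, 200 or 400. Those denominators are assumptions; they show how far the definition matters and do not estimate this trial's uptake.

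Confidence is high that the wording is inconsistent and the denominator undefined. The documents do not show which figure the investigators would report. The consequence is confined to the description of feasibility.

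**What to change.** Use the ratio in all five places: Study Summary, Section 3, Table 1, 4.1 and 7.1. Then:

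- **Denominator.** Patients approached about the study by any route in Protocol 6.3.3 or 6.3.4, and not known to fail a non-volitional criterion (inclusions 1 to 4, the ability part of inclusion 5, exclusions 1, 2 and 4). State that refusal, not agreeing to use the iPad, unwillingness or lack of time, and absence of consent do not remove a patient.
- **Flow.** As far as existing records allow, report approached, declined by reason, screened, ineligible, not enrolled because an LAR or caregiver stayed (on a separate line), and enrolled. Give the number whose eligibility is unknown.
- **Sources.** Name them in Table 1: enrollment records, the screening log (Protocol 6.3.3) and the RA observations on enrollment (Protocol 6.4.1), where they cover the patient.
- **Permission.** Use aggregate counts only for patients who did not consent, and confirm that this use is allowed under the recruitment-only HIPAA waiver.
- **Disclosure.** State that the denominator was clarified after recruitment.

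The cost is SAP wording, one tabulation and a check on permission. The figure will probably be less favourable than 100%. It will also be only as complete as the approach and refusal records: the protocol describes the log as tracking health records accessed and the RA observations as made for each participant, and nowhere says that refusals made to clinic staff were recorded.

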4.2 Other Pre-Specified Outcomes

Acceptability: Participant satisfaction will be measured along multiple dimensions using post-use satisfaction survey with two 5-point Likert response set scales, developed by the research team. Scale 1: Likert scale 1-5, where 1= Very Dissatisfied, and 5= Very Satisfied Scale 2: Likert scale 1-5, where 1= Strongly Disagree, and 5= Strongly Agree

Demand: Demand will be assessed through examining how likely will VOICES be used by patients. To do this, the size of target population of EM victims in the ED will be measured by the % of the patients who self-identified with elder mistreatment and the % who receive the Brief Negotiation Interview (BNI) portion of VOICES.

Practicality: Practicality will be assessed by observing the ease of VOICES use by patients. To do this, a series of steps will be watched to determine the efficiency of implementation measured by the average time (1) to consent & orient participants to the tool and (2) needed to complete VOICES documented by the Research Assistant; and (3) patients perceived time of VOICES as measured on post-survey. Each of these will be reported as part of the overall outcome.

Efficacy of the Brief Negotiation Interview: We will look at how many patients changed their readiness to identify and readiness to disclose after completing the Brief Negotiation Interview (BNI).

Efficacy of Self-Identification on Self-Disclosure: We will explore whether self-identification impacts likelihood of self-disclosure. Effect-size estimation measured by change in the % of patients who disclose among those who self-identified.

Accuracy: To understand the accuracy of the VOICES tool, a preliminary evaluation of the accuracy of VOICES as a screening tool in correctly classifying EM cases that were positive based on social worker assessment, and those referred to Adult Protective Services (APS). The percent correct classification will be reported.

5. RANDOMIZATION

Randomization is not applicable with the single arm design.

6. SAMPLE SIZE

6.1 Sample Size Determination for the Primary Outcome

The sample size was determined based on the practical considerations of time and availability of subjects and the precision by which the targeted feasibility parameters will be estimated. For dichotomous outcomes (e.g., demand, implementation) a sample size of (N=80) will be a sufficient size to estimate a 95% confidence interval around a proportion with a width of no greater than 0.228. For continuous outcomes (e.g., acceptability, time to completion) a sample size of 80 produces a two-sided 95% confidence interval with a distance from the mean to the limits that is equal to 22% of the measure's standard deviation.

7 ANALYTIC PLAN

7.1 Analysis of Primary Outcome:

Implementation in Terms of Participation. Participation will be determined by the ratio of participants who are successfully enrolled to the total number of eligible patients. The numerator, denominator, frequencies and 95% confidence intervals will be reported.

Implementation in Terms of Usage. Usage will be determined by the number of consented participants enrolled in the study who used VOICES to completion. The numerator, denominator, frequencies and 95% confidence intervals will be reported.

7.2 Analysis of Other Pre-Specified Outcomes

Acceptability: Participant satisfaction will be measured along multiple dimensions using post-use satisfaction survey with two 5-point Likert response set scales, developed by the research team. Scale 1: Likert scale 1-5, where 1= Very Dissatisfied, and 5= Very Satisfied Scale 2: Likert scale 1-5, where 1= Strongly Disagree, and 5= Strongly Agree. The means and standard deviations will be reported.

Demand: Demand will be assessed through examining how likely will VOICES be used by patients. To do this, the size of target population of EM victims in the ED will be measured by the % of the patients who self-identified with elder mistreatment and the % who receive the Brief Negotiation Interview (BNI) portion of VOICES. Counts of participants will be reported.

Practicality: Practicality will be assessed by observing the ease of VOICES use by patients. To do this, a series of steps will be watched to determine the efficiency of implementation measured by the average time (1) to consent & orient participants to the tool and (2) needed to complete VOICES documented by the Research Assistant; and (3) patients perceived time of VOICES as measured on post-survey. Each of these will be reported as part of the overall outcome. The means and standard deviations will be reported.

Efficacy of the Brief Negotiation Interview: We will look at how many patients changed their readiness to identify and readiness to disclose after completing the Brief Negotiation Interview (BNI). Counts of participants will be reported.

Efficacy of Self-Identification on Self-Disclosure: We will explore whether self-identification impacts likelihood of self-disclosure. Counts of participants who change willingness to disclose among those that self-identify will be reported.

Accuracy: To understand the accuracy of the VOICES tool, a preliminary evaluation of the accuracy of VOICES as a screening tool in correctly classifying EM cases that were positive based on social worker assessment, and those referred to Adult Protective Services (APS). The percent correct classification will be reported.

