3.2.1 Potential Risks

There are no medical interventions in this study, and direct medical risks are minimal. However, identification of potential EM without adequate safeguards could increase the risk of physical harm, emotional harm, risk of neglect, and financial loss to the victim. In addition, EM identification can potentially lead to adverse events including:

- retaliation of a family member or caregiver,
- an older adult may lose the caregiver or be abandoned by a caregiver, and a family member or paid caregiver may be arrested / incarcerated,
- discharge of a patient to a long-term care or skilled nursing facility, which they may not be able to afford,
- distress/anxiety during and/or after using the VOICES tool is a potential risk given the complex emotions typically associated with this phenomenon.
- there is a risk of compromised security of personal information.

Many of these adverse events would likely occur as a result of the mandatory report to Connecticut Protective Services for the Elderly (PSE) that the care team (case manager, clinician, nurses, and attendings) would make. However, during this study the care team is NOT expected to discover information that will require them to make a report to PSE.

Minimizing Risks:

Risks will be minimized through appropriate participant exclusions and close medical supervision throughout the protocol. We will inform all participants that there is a chance that they may experience adverse events due to the identification of EM by participating in the study and that their participation is voluntary. We will also remind participants that they can discontinue participation at any time.

In Summary: VOICES' goal is to help identify cases of EM. The subsequent procedures for the EM identification are important but are similar to the case when a provider identify suspicion of EM during normal clinical care:

- all patients who screen positive with the VOICES tool will be reviewed and assessed by YIMA care team.
- while the research team recognizes that the EM identified through the VOICES tool may lead to risks for patients that are usually associated with EM identification, we anticipate that the care team response will minimize the possible adverse events due to the EM identification.

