- We will train all RAs to detect common signs of distress and anxiety. If any are even suspected of being observed, the care team at YIMA, will be contacted immediately for consultation and next steps, which could include counseling, referrals, or a psychiatric evaluation.
- If the older adult screens positive on the VOICES for EM or the older adult wants to self-disclose EM, the RA will notify the care team in the YIMA that there is suspicion of EM. Also, if the tool fails to identify EM but the patient would like to disclose EM, the RA will notify the care team. The RA will stay with the participant until a member of the care team arrives and implements existing protocols for handling EM identification.

- The care team can address each patient's concerns around reporting, immediate safety concerns, and any concerns for retaliation or abandonment. If the assessment indicates suspicion of abuse, and the case gets reported to PSE, usually PSE will arrive within 12 hours to take care of the case. While waiting for PSE, the health care team members will discuss safety issues with the patient.
- We will protect against psychological distress by informing all participants that there is a chance that they may experience some negative emotions while completing the surveys, after completing survey, or when they leave the hospital, but that they do not have to answer questions that they find distressing. We will also remind participants that they can discontinue participation at any time. We will also provide all older adults that we approach with the brochure on resources for aging well that also include free referral line. These options will be discussed with participants during initial recruitment.

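### VOICES accuracy is judged by an assessment that begins with a notice of suspected mistreatment, and the planned single percentage does not say how cases the tool missed are counted

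*SAP*

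**What the plan says.** **The measure.** SAP 4.2 and 7.2 describe the Accuracy outcome as "a preliminary evaluation of the accuracy of VOICES as a screening tool in correctly classifying EM cases that were positive based on social worker assessment", together with cases referred to APS. The analysis is one sentence: "The percent correct classification will be reported". Neither section gives a numerator, a denominator or an interval.

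Table 1 in SAP section 4 words the same outcome differently: "Measured as percent of classified EM cases that were positive based on social worker assessment, and those referred to Adult Protective Services (APS". Its source column reads: "Measured by the outcome of the social worker assessment and by the outcome APS evaluation". Read naturally, Table 1 starts from the cases that the tool classified as EM and asks how many were borne out, which is a positive predictive value.

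**How a participant comes to be assessed.** Protocol 3.2.1 says that "all patients who screen positive with the VOICES tool will be reviewed and assessed by YIMA care team". The trigger is that "the older adult screens positive on the VOICES for EM or the older adult wants to self-disclose EM, the RA will notify" the care team; more exactly, "the RA will notify the care team in the YIMA that there is suspicion of EM". A further route is stated alongside: "if the tool fails to identify EM but the patient would like to disclose EM, the RA will notify the care team". Protocol 6.3.5 repeats the rule as a positive screen or a wish to self-report. Protocol 3.2.1 adds that the physician is told of any suspicion, then evaluates and decides whether a report to protective services is needed.

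Neither document describes an assessor kept unaware of the tool result, or any assessment of participants who screen negative and do not disclose.

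**The concern.** A percent correct figure takes the reference result as a verdict reached independently of the test. Here the assessment happens because the test was positive or the person wished to disclose, and the team is told that EM is suspected before it starts. An alerted assessor may be readier to confirm. Counting a protective-services referral as a positive does not remove the difficulty, because under the protocol the alerted team decides on that referral.

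The second difficulty is one of definition. The assessed group can contain people whom the tool flagged and people whom it missed. Without a stated denominator, the reader cannot tell whether the missed cases are left out, counted against the tool or counted as found.

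Protocol 5.1 says that the study is to guide changes to VOICES for a future pilot, and Protocol 7.18 hopes that it will inform national screening guidelines. A figure labelled accuracy could be carried forward as evidence of screening performance when it is confirmation by people who had been alerted.

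**Working it through.** **1. The plan's own precision figure.** SAP 6.1 gives a 95% CI width of at most 0.228 for a proportion with N = 80. The exact (Clopper-Pearson) interval for 40/80 runs from 0.386 to 0.614, a width of 0.2279, so the figure reproduces. It applies to a denominator of 80. The Accuracy denominator is the number assessed, which the documents do not give.

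**2. Who has a reference result.**

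| VOICES result | Wishes to disclose | Assessment described? | Assessor told of suspicion? |
|---|---|---|---|
| Positive | Yes or no | Yes | Yes (care team) |
| Negative | Yes | Yes | Yes (care team) |
| Negative | No | No | – |

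The third row has no reference result, so a percent correct over all 80 cannot be calculated. Only figures among referred participants can be.

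**3. Illustration of direction.** The documents give no prevalence, sensitivity, specificity or referral counts, so all rates here are assumptions. Take N = 80, prevalence 10%, sensitivity 0.70 and specificity 0.90.

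- Cases: 80 × 0.10 = 8. True positives 8 × 0.70 = 5.6; false negatives 2.4.
- Non-cases: 72. False positives 72 × 0.10 = 7.2; true negatives 64.8.
- Tool-positives: 5.6 + 7.2 = 12.8. Share truly EM: 5.6/12.8 = 0.438.

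*Alerted assessor.* Let a fraction b of false positives be confirmed because suspicion was announced. The observed share is (5.6 + 7.2b)/12.8:

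| b | Confirmed | Share of tool-positives confirmed |
|---|---|---|
| 0 | 5.60 | 0.438 |
| 0.10 | 6.32 | 0.494 |
| 0.25 | 7.40 | 0.578 |
| 0.50 | 9.20 | 0.719 |

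*Tool-negative disclosers.* Let 30% of the false negatives disclose and be confirmed: 0.30 × 2.4 = 0.72. Set b = 0.

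- Counted as misses: 5.6/(12.8 + 0.72) = 5.6/13.52 = 0.414, lower than 0.438.
- Counted as detections: (5.6 + 0.72)/13.52 = 6.32/13.52 = 0.467, higher than 0.438.

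These directions do not depend on the chosen rates. Adding people to the denominator alone lowers a proportion; adding the same number to the numerator and denominator of a proportion below 1 raises it.

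**4. Range.** With specificity held at 0.90, prevalence from 5% to 20% and sensitivity of 0.70 or 0.80, the share with b = 0 runs from 0.269 to 0.667. With b = 0.50 it runs from 0.635 to 0.833.

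**5. Precision of the corrected measure.** With about 13 tool-positives (12.8 rounded) and 6 confirmed, the exact 95% CI is 0.192 to 0.749, a width of 0.556 against the 0.228 of SAP 6.1.

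**The case against.** The strongest reply is that Accuracy is a preliminary, non-primary outcome in a feasibility study of 80 people, and that Table 1 already points to a sensible quantity. If the denominator is the tool-classified cases, tool-negative disclosers never enter and there is no mixing. The SAP does not state that it pools the routes. This stands in part: the defect is that 4.2 and 7.2 name a different quantity from Table 1 and leave the denominator open.

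It can also be said that no document shows the social worker being alerted. The care team listed in Protocol 3.2.1 is case manager, clinician, nurses and attendings, and the SAP does not say what the social worker or APS is told. That stands too. The alert to the care team is documented; its reach to the social worker is an inference, reasonable because no other route to assessment is described.

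A reader might go further and infer that mixing in disclosers inflates agreement in the tool's favour. The documents do not support this, since confirmed tool-negative disclosers lower agreement if counted as misses.

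A reader might also treat tool-positives who disclose as contamination. Suppose that, of 12 tool-positives, 4 disclose and all 4 are confirmed, and 4 of the other 8 are confirmed. The shares are 8/12 = 67% overall and 4/8 = 50% without the disclosers. That gap comes from removing confirmed cases; it does not measure bias. Prompting self-disclosure is part of what VOICES is meant to do, so a headline limited to tool-positives who did not disclose would be a choice of a different estimand.

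**Conclusion.** The point holds as a risk of bias together with an undefined measure. The assessment is triggered by the tool result or by a wish to disclose. The care team knows that EM is suspected, and no masking is described. That risks over-confirming tool-positives by an amount the documents do not allow anyone to derive; the rise from 0.438 to between 0.494 and 0.719 rests wholly on assumed rates. The effect of tool-negative disclosers can go either way and depends on a counting rule that the SAP does not state. It would be too strong to say that the reported figure is biased toward the tool, or that the social worker is known to be unmasked. The primary outcomes, participation and usage, are untouched.

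**What to change.** In SAP 4.2 and 7.2, to agree with Table 1:

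1. Report the share of all VOICES-positive participants confirmed by the social worker or APS, with numerator, denominator and 95% CI. Say whether APS confirmation means referral or the outcome of the APS evaluation, since Table 1 mentions both.
2. Report separately, as cases the tool missed, the number of tool-negative participants who disclosed and were confirmed.
3. Replace the labels *accuracy* and *percent correct classification* with *confirmation among referred participants by assessors aware of suspected EM*. State that tool-negatives who did not disclose had no assessment.
4. Optionally, split tool-positives by whether they disclosed, as description only and where records allow. Table 1 has disclosure measured by the tool, and Protocol 6.4.1 lists RA observations as a data source. Protocol 7.7 does not list a notification log among the study records, so its availability needs to be confirmed first.

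The cost is SAP wording and a small table. The cells will be small, the interval wide and the claim more modest. The SAP, revised 5/16/2023, says that the 80 participants were already recruited, so masked assessment cannot be added by an analysis change, and this fix describes the assessor problem without removing it. The notification rule does not change.
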